# 7.3.3 Laboratory Safety Tests

## **Blood Sampling**

The *actual* date and time of any blood sampling must be recorded in the CRF, on the label of the laboratory tubes and on the corresponding laboratory shipment forms.

If several blood samples have to be taken at one time point, the blood sampling will be done in the following sequence:

- 1. Haematology: RBC count, WBC count, haemoglobin, haematocrit, platelet count (EDTA blood)
- 2. Coagulation: FVIII plasma level and FVIII inhibitor control (citrated plasma)
- 3. Biochemistry: ALT, AST, serum creatinine (serum)
- 4. RNA expression analysis (optional) (whole blood, RNAse-free conditions)
- 5. Immunogenotyping: gene mutation analysis (mandatory), HLA-typing, immune response gene profiling, FVIII ethnic haplotype determination (optional), (EDTA blood)
- 6. In vitro immunogenicity of FVIII products (optional) (citrated blood)

It is essential that blood sampling after the injection of *Human-cl rhFVIII* is done from the other arm.

Blood samples taken for citrate plasma will be centrifuged after collection for 15 to 20 minutes at 1500 to 2000 g (about 3000 rpm). Aliquots of the supernatant are subsequently transferred into the tubes provided by the central laboratory (pre-labelled with date and time point of sampling, type of sample, patient identification and study number) and stored, respectively shipped under adequate conditions.

# EDTA Blood

A 1 mL sample (or less, as required by the local laboratory) of EDTA blood will be collected for the measurement of haematology parameters (RBC count, WBC count, haemoglobin, haematocrit, platelet count). All haematology tests are to be done at the local laboratory.

A further 5 mL sample will be collected for the FVIII gene mutation analysis and the optional further immunogenotyping (HLA-typing, immune response gene profiling and FVIII ethnic haplotype analysis). The immunogenotyping will be done at the University laboratory of [name] in Bonn, Germany. The blood samples will be stored at  $\leq$ -70°C and shipped to the central laboratory on dry-ice.

## Citrated Plasma

For the analysis of coagulation factor and inhibitor screen, both performed in the central laboratory in the US, a maximum of around 2 mL of citrated blood will be collected. After collection and centrifugation, the plasma will be aliquoted into cryo-resistant tubes. Samples will be stored at  $\leq$ -70°C and shipped to the central laboratory on dry-ice.

For analysis performed locally, e.g. at screening and pre-, intra, and post-surgery, citrated blood as required by the local laboratory will be collected and processed in accordance with local requirements.

From patients developing an inhibitor to FVIII, and agree to participate in the epitope mapping sub-study, a further pre-ITI initiation 2 mL citrated blood sample ( $2 \times 0.5$  mL citrated plasma) is needed. After ITI initiation two further blood sampling time points are recommended: as close as possible after the peak inhibitor level, as well as after inhibitor eradication.

## Serum

For the determination of clinical chemistry (ALT, AST, serum creatinine) a blood sample of about 0.5 mL (or less, as required by the local laboratory) will be collected. All tests are to be done at the local laboratory.

## Citrated blood

If the (optional) analysis of immunogenicity of FVIII products (*in vitro* T cell assay) is to be performed, a blood sample of exactly 5 mL needs to be collected. Samples will be kept at room temperature and are immediately shipped to Antitope Ltd. at ambient temperature. The samples must arrive at the central laboratory within 24 hours after collection.

# Whole blood (RNAse-free conditions)

If the RNA expression analysis is performed, about 1.0 mL of blood will be collected into an sterile (RNAase & DNase-free) syringe and directly transferred into a customised PAXGene tube (provided by the central laboratory and pre-labelled with date and time point of sampling, type of sample, patient identification and study number). Sample should be kept upright for a minimum of 2 hours at room temperature  $(18 - 25^{\circ}C)$  following blood sampling (maximum time 72 h). Samples can be stored at -20°C or -70°C and shipped to the central laboratory on dry ice. See Appendix 2 for a detailed sampling protocol.

The "Ethical Considerations for Clinical Trials on Medicinal Products conducted with the Paediatric Population" are followed during the conduct of GENA-05. The Committee recommends the below blood volume limits for sampling in neonates:

Per individual, the trial-related blood loss should not exceed 3 % of the total blood volume during a period of four weeks, and should not exceed 1% at any single time. The total volume of blood is estimated at 80 to 90 ml/kg body weight; 3% is 2.4 ml blood per kg body weight.

Time-points and required blood volume needs for laboratory parameters are as follows (all optional blood samplings are greyed out):

	Screening Follow-Up			Surgery	ITI	
	(Baseline)	Every 3-4 EDs (until ED 20)	Every 10-12 EDs (after ED 20) / 3-Months Visits	Completion Visit	(Pre-, intra- and post-surgery)	Recovery / PK Visits
FVIII inhibitor screen (citrated blood/plasma) -central laboratory-US	2 mL/0.7 mL	2 mL/0.7 mL (5-6 x)	2 mL/0.7 mL	2 mL/0.7 mL		2 mL/0.7 mL
Haematology (local laboratory)	~1 mL EDTA blood		~1 mL EDTA blood	~1 mL EDTA blood	~1 mL EDTA blood	
Clinical chemistry (local laboratory)	~0.5 mL serum		~0.5 mL serum	~0.5 mL serum	~0.5 mL serum	
FVIII:C (3 samples if recovery determination is done) (citrated blood/plasma) -central laboratory-US	1.4 mL/0.7 mL		1.4 mL/0.7 mL		1.4 mL/0.7 mL	1.4 mL/0.7 mL
FVIII gene mutation analysis Optional: Immunogeno- typing: HLA-typing, immune response gene profiling, FVIII ethnic haplotype determination -central laboratory-Germany			5.0 mL (2 EDTA			
RNA expression analysis* ( § ITI baseline, 2 and 4 weeks after ITI start, monthly until month 6) -central laboratory-UK	1.0 mL whole blood	1.0 mL # whole blood				1.0 mL #§
In vitro immunogenicity* -central laboratory-UK	5.0 mL † citrated blood or Li heparin					
Epitope mapping in case of inhibitor development ‡ central laboratory-Germany						2.0 mL citrated blood (preferred at 3 time-points)

Table 8         Time-Points and Blood Volume for Laboratory Para
--

\* Optional analyses. ‡ If *in vivo* recovery analysis is to be performed. † Suggested timing of analyses. # This analysis should be performed at the scheduled study visits whenever possible.

All treatment-emergent rise in AST or ALT to  $>3 \times$  ULN will be followed by assessing liver function tests until their return to normal; or (in case of *a priori* increased values) until their return to the individual's baseline; or until a definite diagnosis is determined.

If the abnormal values persist for more than 1 week, viral serology (hepatitis B virus, hepatitis C virus) and PCR testing will be performed by the local laboratory to rule out hepatitis B and C. In addition, PCR testing of the corresponding batches will be performed by the central lab.

The Investigator must assess the clinical significance of abnormal laboratory values outside the normal range as specified by the reference laboratory. Any clinically significant abnormalities

Amended Study Protocol CONF No. GENA-05

should be fully investigated.

Only laboratory abnormalities that have been rated as being clinically significant will be documented as AEs/ADRs. Clinically significant is defined as any laboratory abnormality that the Investigator feels is of clinical concern, and/or requires medical intervention and/or follow-up. Additional tests and other evaluations required to establish the significance, or aetiology of an abnormal result or to monitor the course of an AE should be obtained if clinically indicated. Any abnormal laboratory value that persists should be followed until resolution or for 14 days after the final study visit, whichever occurs first. Preferably, clinically significant lab abnormalities should be medically diagnosed and entered as a diagnosis into the AE form, if not already present at baseline.

The following table summarises all test parameters and the laboratory responsible for analysis:

Test	Material needed	Responsible laboratory		
FVIII:C* (one-stage and chromogenic assay)	Citrated plasma	LabCorp Clinical Trials Laboratory Services [name]		
Inhibitors to FVIII (modified Bethesda assay - Nijmegen modification)	Citrated plasma			
Haematology	EDTA blood	Local laboratory		
Clinical chemistry	Serum	Local laboratory		
Immunogenotyping (FVIII gene mutation analysis, HLA-typing ‡ , immune response gene profiling ‡ and FVIII ethnic haplotype ‡ )	EDTA blood	[name] Institute of Experimental Haematology and Transfusion Medicine [name]		
RNA expression analysis ‡	Whole blood (RNAse-free conditions)	[name] and [name] Dept of Haematology Laboratory 4 th Floor, Pathology and Pharmacy building Royal London Hospital Barts and The London School of Medicine and Dentistry [name]		
In vitro immunogenicity of FVIII products ‡	Blood (citrated or heparinised)	Antitope Ltd Business Development Group [name]		
Epitope mapping ‡	Citrated plasma	[name] Institute of Experimental Haematology and Transfusion Medicine [name]		
PCR testing of Human-cl rhFVIII batches†	Human-cl rhFVIII	Octapharma AB [name]		

Table 9Test Parameters and Laboratories

\* Performed locally at screening and when required, e.g. pre-, intra- and post-surgery.

‡Optional investigations.

† Performed if abnormal AST or ALT values persist for more than 1 week.

All remaining serum and plasma volumes will be labelled and stored as retention samples at the central laboratory for at least 2 years after the completion of the study and until Octapharma's written authorisation to destroy these samples.

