# **RNA Expression Transportation and Storage Protocol**

- Keep sample upright for 4-6 hours at room temperature (18 25°C) following blood sampling, prior to freezing. Early freezing of samples will substantially decrease the RNA yield.
- 2) Freeze sample at -70°C in a wire rack (not a stryofoam tray as this may lead to sample tubes cracking).

- Transport frozen PAXgene stabilised RNA study samples to LabCorp (LabCorp Clinical Trials, Laboratory Services, [name]) on dry ice.
- 4) RNA Samples kept at -70°C will be stable for a period of up to 60 months (6).

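### Protocol 7.3.3 permits freezing RNA samples after 2 hours and storing them at -20 °C, while Appendix 2 asks for 4-6 hours and -70 °C and warns against early freezing

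*Protocol*

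**What the plan says.** Two parts of the protocol tell sites how to handle the RNA expression sample after it is drawn.

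- **Section 7.3.3, Whole blood (RNAse-free conditions).** The hold is open-ended upwards from 2 hours: "Sample should be kept upright for a minimum of 2 hours at room temperature". The cap follows: "following blood sampling (maximum time 72 h". Two storage temperatures are allowed: "Samples can be stored at -20°C or -70°C and shipped to the central laboratory on dry ice". The paragraph closes with a pointer: "See Appendix 2 for a detailed sampling protocol".
- **Appendix 2, RNA Expression Transportation and Storage Protocol.** The hold before freezing is narrower: "Keep sample upright for 4-6 hours at room temperature". The reason is given next: "Early freezing of samples will substantially decrease the RNA yield". One freezing temperature is named: "Freeze sample at -70°C in a wire rack". Stability is stated for that temperature only: "RNA Samples kept at -70°C will be stable for a period of up to 60 months".

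Section 7.4.1.2 also names Appendix 2 as the place for the full sub-study protocol. Neither document says which text prevails if they differ.

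**The concern.** An appendix may add detail to the body of a protocol. Here it does more: it narrows the permitted hold at both ends and drops a storage temperature that the body allows. A site can therefore comply with 7.3.3 and still freeze earlier than Appendix 2 permits, with the loss of yield that the appendix warns of.

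What is at stake is the quality of the RNA samples. Appendix 2 looks for expression signatures that predict inhibitor formation or failure of immune tolerance induction. It stresses that mRNA is unstable and has to be stabilised at collection. A poor first sample cannot be replaced, because it must precede the first FVIII exposure. Handling that differs between visits or sites would be mixed into the comparisons the sub-study is meant to make.

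**Working it through.** The plan gives no statistical figure on this point, so there is nothing to reproduce. The check is to set the two instructions side by side.

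| Item | Section 7.3.3 | Appendix 2 |
|---|---|---|
| Shortest hold at room temperature | 2 h | 4 h |
| Longest hold at room temperature | 72 h | 6 h |
| Storage temperature | -20 °C or -70 °C | -70 °C |
| Stated harm | none | early freezing lowers RNA yield |
| Stated stability | none | 60 months, at -70 °C |

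**Step 1: can both texts be met?** Yes. The 4-6 h window lies inside 2-72 h, and -70 °C is one of the two temperatures in 7.3.3. A site that follows Appendix 2 complies with both.

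**Step 2: what does 7.3.3 allow that Appendix 2 does not?** The window in 7.3.3 is 72 - 2 = 70 h wide, and the window in Appendix 2 is 6 - 4 = 2 h wide. The remaining 68 h fall into two parts, and the temperature makes a third difference:

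- freezing from 2 h to just under 4 h (4 - 2 = 2 h);
- holding beyond 6 h, up to 72 h (72 - 6 = 66 h);
- storing at -20 °C.

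**Step 3: which of these do the documents call harmful?**

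- *Freezing before 4 h.* The warning stands directly after the 4-6 h instruction, so its natural reading is freezing before that window. The size of the loss is not given.
- *Holding beyond 6 h.* No harm is stated. The blood goes straight into a stabilising reagent.
- *Storing at -20 °C.* No harm is stated and no stability period is given. Storage life at this temperature is undocumented, which is not the same as shown to be inadequate.

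The documents thus support harm for one of the three differences, without a size, and that harm is to RNA yield. They do not say what early freezing does to the expression profile.

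**Step 4: what depends on the data?** RNA expression is optional and is neither a primary nor a secondary endpoint. Protocol 9.2.2 plans descriptive statistics for it. SAP sections 1, 3.4.8 and 9.1 exclude it from analysis under the SAP, although SAP section 13 still lists a data listing (16.2.4.5). The data are meant to be used, but no conclusion on inhibitors, efficacy or safety rests on them.

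**The case against.** The strongest reply is that sites are sent to Appendix 2 twice, by 7.3.3 itself and by 7.4.1.2, and that a site which goes there meets both texts. This stands in part. It means that departures *can* occur, and it gives no ground for saying that they *will*. It does not remove the conflict, because the body text states a complete rule of its own and no order of precedence is given.

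A second reply is that the sub-study looks at changes within a patient, so a practice that stays constant at a site would partly cancel. That is fair. It gives no protection when handling varies between visits, and the documents do not show that a loss of yield would cancel.

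Three stronger readings are tempting and are not supported:

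- *A 36-fold difference in handling.* The ratio 72/2 = 36 describes the width of one permitted window. It is not an effect on the samples, and the stated harm concerns only early freezing.
- *Non-comparable samples across about 40 sites.* That is the planned number of centres for the whole study. The number taking part in the optional RNA sub-study is not given.
- *Damage from -20 °C or from a long hold.* Neither is stated anywhere in the documents.

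**Conclusion.** The inconsistency is real, and 7.3.3 is wrong as written, with low materiality. A site relying on 7.3.3 alone can freeze between 2 and 4 hours, which by the protocol's own warning lowers RNA yield by an amount the documents do not quantify. The longer hold and the -20 °C option are further mismatches without a documented harm; for -20 °C there is also no stated stability period.

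The effect is confined to the optional RNA sub-study. The inhibitor endpoint and the safety assessment are unaffected.

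The conclusion assumes that early freezing means freezing before the 4-6 hour window of Appendix 2. How many samples, if any, were handled outside that window cannot be told from the documents.

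**What to change.** - **Text.** Replace the handling rule in 7.3.3 with that of Appendix 2: upright at room temperature for 4-6 hours, then -70 °C. Samples already handled under Appendix 2 remain compliant, since its conditions lie inside the present 7.3.3.
- **Record.** Add time of freezing and storage temperature to the shipment form. Section 7.3.3 already requires the actual sampling date and time in the CRF, on the tube and on the shipment form, so the length of the hold then follows by subtraction.
- **Use.** Flag samples frozen outside 4-6 hours or stored at another temperature, and leave them out in a sensitivity analysis of the RNA data.
- **Samples already taken.** Version 05 is dated 01-Feb-2018, with completion planned for the fourth quarter of 2018 apart from continuing ITI patients. Many samples from the first 20 exposure days have therefore probably been drawn. For these, new wording cannot help; recover the handling details from site records where they exist.

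The cost is a short amendment of the text and the extra entries on the shipment form. The -70 °C requirement should add little burden, because 7.3.3 already asks for storage at or below -70 °C for the gene mutation and central coagulation samples.

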## **4 STUDY POPULATION**

## 4.1 **Population Base**

Male patients (mainly new-borns or infants, although no age limitation is given) with severe Haemophilia A (FVIII:C < 1%), without any previous FVIII concentrate treatment or any previous treatment with other FVIII-containing blood products will be enrolled into the study.

In total, 100 PUPs will be enrolled by approximately 40 centres from around the world.

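### Taken in one draw, the fixed screening volumes in Table 8 exceed the protocol's own 1% blood-loss limit in newborns, and the text and Table 8 disagree on the citrated volume

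*Protocol*

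**What the plan says.** Protocol section 7.3.3, in the part on whole blood, states that the paediatric ethics guidance and its blood-volume limits "are followed during the conduct of GENA-05". It introduces the limits with "The Committee recommends the below blood volume limits for sampling in neonates". They are that "the trial-related blood loss should not exceed 3 % of the total blood volume during a period of four weeks", and that it "should not exceed 1% at any single time". The basis is given as "The total volume of blood is estimated at 80 to 90 ml/kg body weight; 3% is 2.4 ml blood per kg body weight". The 1% limit is not converted to mL/kg.

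Table 8, directly below, lists the volumes needed. At screening these are 2 mL for the inhibitor screen, 1.4 mL for FVIII:C, about 1 mL for haematology and about 0.5 mL for chemistry. None depends on body weight, and no total per visit is shown. Optional samples come on top: 1 mL for RNA expression and 5 mL for the in vitro test.

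The EDTA paragraph adds: "A further 5 mL sample will be collected for the FVIII gene mutation analysis" (the same tube also serves the optional immunogenotyping). The gene analysis is mandatory. Table 1 places it at screening; its footnote and section 7.4.1.3 allow any time in the study but steer sites towards scheduled visits.

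For the central factor and inhibitor tests together, the citrated plasma paragraph says "a maximum of around 2 mL of citrated blood will be collected".

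Section 4.1 describes the patients as "mainly new-borns or infants, although no age limitation is given". No minimum weight is set.

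**The concern.** One section both adopts a limit that scales with body weight and prescribes volumes that do not. For a small enough child the two must collide, and the protocol expects to enrol newborns. It is a stated safety limit, so a site that draws the listed screening set in one venepuncture could breach a commitment the protocol makes on the patient's behalf. A site that notices has to decide for itself which samples to split, postpone or drop. The two citrated volumes add to this, because a site cannot tell from the protocol what the screening draw should total.

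**Working it through.** **Reproducing the protocol's figure.** 3% of 80 mL/kg is 0.03 x 80 = 2.4 mL/kg, which matches the stated value. It uses the low end of the range; 90 mL/kg gives 2.7 mL/kg. On the same basis 1% is 0.01 x 80 = 0.8 mL/kg, or 0.9 mL/kg at 90.

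**Volumes.**
- Core screening set, Table 8: 2 + 1.4 + 1 + 0.5 = 4.9 mL.
- The same set with citrated blood held to about 2 mL: 2 + 1 + 0.5 = 3.5 mL.
- Gene sample: 5 mL.

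**Lowest weight at which one draw stays within 1%** = volume / 0.9 to volume / 0.8.

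| Single draw | mL | Lowest weight within 1% (kg) |
|---|---|---|
| Inhibitor screen alone | 2 | 2.2-2.5 |
| Core screening, about 2 mL citrated | 3.5 | 3.9-4.4 |
| Core screening, Table 8 | 4.9 | 5.4-6.1 |
| Gene sample alone | 5 | 5.6-6.25 |
| Gene sample + inhibitor visit | 7 | 7.8-8.75 |
| Gene sample + core screening | 9.9 | 11.0-12.4 |

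**At newborn weights (assumption; the documents give none).** For 3 to 3.5 kg the 1% limit runs from 0.8 x 3 = 2.4 mL to 0.9 x 3.5 = 3.15 mL. As a share of blood volume over that range:
- 3.5 mL is 1.1-1.5%.
- 4.9 mL is 1.6-2.0%.
- 5 mL is 1.6-2.1%.

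At 4 kg the limit is 3.2-3.6 mL. The 3.5 mL reading is then borderline (0.97-1.09%), and 4.9 mL still exceeds the limit (1.4-1.5%).

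**Four-week limit, if draws are split over days.** Lowest weight = volume / 2.7 to volume / 2.4. For 4.9 mL this is 1.8-2.0 kg; for 9.9 mL it is 3.7-4.1 kg. At 3 to 3.5 kg the four-week allowance is 2.4 x 3 = 7.2 mL to 2.7 x 3.5 = 9.45 mL. The core set fits if split. Core set plus gene sample does not, so the gene sample would have to come later. Any 2 mL follow-up draws in the same four weeks also count.

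**Citrated volume, no weight assumption.** Table 8 gives 2 + 1.4 = 3.4 mL for the two central tests at screening. The text gives about 2 mL for both. The difference is 1.4 mL.

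**The case against.** The strongest case is that the protocol already leaves enough room to comply.
- The gene sample may be taken at any time, participation can last up to five years, and a deferred draw is taken from a heavier child.
- The RNA and in vitro samples are optional.
- The EDTA and serum paragraphs let the local laboratory take less for haematology and chemistry.
- Nothing requires one venepuncture for the whole screening set.
- The 2 mL inhibitor draw alone complies from 2.5 kg.

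All of this stands. A reader might infer that sites cannot satisfy both Table 8 and the limit, and the documents do not support that: splitting and deferral are open to them.

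Two further inferences also go too far. The first is that the limit is broken in most infants, up to 12 kg. That takes a limit worded for neonates to older children, and counts a sample that need not be drawn at screening. The Table 8 entry for the gene sample is cut off in the text available, so its column cannot be read. The second is that the primary analysis is damaged through lost baseline inhibitor tests. The blood-sampling sequence in section 7.3.3 puts coagulation second, and immunogenotyping and the in vitro test last. Under SAP section 5.1 a missing baseline test removes a patient from the per-protocol set only if the first result after exposure is positive, and the ITT population is the most relevant one for immunogenicity. No such damage is shown.

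The 4.9 mL total is also the upper reading. The footnote to Table 9 has FVIII:C done locally at screening, so the central 1.4 mL is uncertain there.

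What the objection does not remove is the single draw as written. Even at 3.5 mL it exceeds the limit at 3 to 3.5 kg, and no passage gives a visit total, a priority order or an instruction to split or defer. The two citrated volumes remain in conflict on any view.

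**Conclusion.** The point holds as an internal contradiction; the section is wrong as written. In a single draw, core screening exceeds the adopted 1% limit below about 5.4-6.1 kg on Table 8's volumes and below about 3.9-4.4 kg on the text's citrated volume. The mandatory gene sample alone exceeds it below about 5.6-6.25 kg. The ranges reflect 90 and 80 mL/kg.

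The claim that newborns are affected rests on an assumed weight of 3-3.5 kg and on the neonatal wording of the limit. How many enrolled patients fall below the thresholds cannot be judged from the documents. For infants past the neonatal period the thresholds show where the same percentage would bind, and are not a breach of the limit as worded. The disagreement on citrated volume needs no assumption.

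**What to change.** In Protocol section 7.3.3:
- Add a row to Table 8 with the total volume per visit, and show it against the protocol's own 1% and 3% limits.
- State that samples the protocol already makes optional or allows at a later time (gene analysis, immunogenotyping, RNA expression, in vitro test) need not be drawn at a visit where the total would exceed a limit. The sponsor should set the rule; this review proposes no weight threshold.
- Make the citrated plasma paragraph and Table 8 give one volume, and say whether FVIII:C at screening is local, central or both.

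The cost is wording and one table row, in an amendment or the laboratory manual, and some genetic samples arriving later. No endpoint or analysis changes. The current version is dated February 2018 with completion planned for the fourth quarter of 2018, so many screening draws may already be past. The change would then mainly serve remaining visits and any gene samples still outstanding.
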